## 6.3 Dose modifications for toxicities

### 6.3.1 Dose modification and dose interruption

For participants who do not tolerate the protocol-specified dosing schedule due to drug related toxicities, dose interruptions and/or reductions are recommended in order to allow participants to continue the study treatment. For the dose escalation part of the study, dose reductions during cycle 1 are only allowed if a DLT is observed and recorded.

Table 6-7 provides recommendations for dose modification and dose interruption (i.e., interruption and re-initiation criteria for nazartinib and capmatinib treatment).

Refer to Table 6-5 and Table 6-6 for recommended dose reduction steps for the Phase II part of the study.

If, due to study drug related toxicity, a participant requires a dose interruption of >21 days from the intended day of the next scheduled dose, then the participant must be discontinued from the study treatment unless described otherwise.

Each participant is only allowed two dose reductions on each drug. In addition, a participant must discontinue treatment with nazartinib and capmatinib if, after treatment is resumed at a lower dose, the toxicity recurs with the same or worse severity.

Exceptions on dose interruptions and modifications can be made on a case by case basis after discussion with Novartis and Investigator.

In exceptional cases, after discussion with Novartis, participants may be allowed to continue treatment or resume treatment with only one of the investigational drugs.

All dose interruptions or modifications must be recorded on the Dosage Administration Record CRF.

In case of study treatment interruption, visit schedule should still be followed and assessments performed as per Table 7-1 and Table 7-2.

After dose modification, re-escalation to a previous dose level is not permitted apart from the exceptional cases described in Table 6-14 and Table 6-15.

Events not included in the study protocol or the reference guidance documents should be managed according to local practices.

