**Table 6-6 Dose Reduction steps for nazartinib**

Dose level	Proposed daily dose of nazartinib
0	nazartinib 100 mg q.d.
-1	nazartinib 75 mg q.d.
-2	nazartinib 50 mg q.d.

Note: dose reduction should be based on the worst toxicity demonstrated at the last dose

**Table 6-7 Criteria for dose reduction, interruption and re-initiation of nazartinib and capmatinib for adverse drug reaction**

Worst toxicity CTCAEa Grade (value)	Recommendation
HEMATOLOGICAL	
Neutrophil count decreased (ANC) Neutropenia	
Grade 1 (ANC < LLN - 1500/mm  ; < LLN - 1.5 x 10  /L)	Maintain dose levels of nazartinib and capmatinib
Grade 2 (ANC < 1500 - 1000/mm  ; < 1.5 - 1.0 x 10  /L)	Maintain dose levels of nazartinib and capmatinib
Grade 3 (ANC <1000 – 500/mm  )	
Omit study treatment until resolved to ≤ grade 2, then resume nazartinib at the same dose level:
 
 
• If fully resolved in ≤ 7 days, then resume capmatinib at same dose level
 
• If fully resolved in > 7 days, then resume capmatinib at ↓ 1 dose level
 
• If recurrence of grade 3 toxicity on maintained dose of nazartinib and ↓ 1 dose level of capmatinib, omit study treatment until resolved to ≤ grade 2, then resume nazartinib at ↓ 1 dose level and the same dose level of capmatinib (i.e., both study drugs ↓ 1 dose level from dose levels at initial occurrence of grade 3 AE)
 
• If recurrence of grade 3 during nazartinib monotherapy, omit study treatment until resolved to ≤ grade 2, then resume nazartinib at ↓ 1 dose level
 
• If no recurrence of grade 3 toxicity after 7 days of nazartinib monotherapy at ↓ 1 dose level, resume capmatinib at same dose level
 

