Grade 4 (ANC < 500/mm  )	
Omit study treatment until resolved, then resume nazartinib at the same dose level
 
 
• If no recurrence of grade 3 or higher toxicity after 7 days of nazartinib monotherapy, resume capmatinib at ↓ 1 dose level
 
• If recurrence of grade 3 or higher toxicity on maintained dose level of nazartinib and ↓ 1 dose level of capmatinib, omit study treatment until resolved to ≤ grade 2, then resume nazartinib at ↓ 1 dose level and capmatinib at the same dose level (i.e., both study drugs ↓ 1 dose level from levels at initial occurrence of grade 4 AE)
 
• If recurrence of grade 3 or higher toxicity during nazartinib monotherapy, omit study treatment until resolved to ≤ grade 2, then resume nazartinib at ↓ 1 dose level
 
• If no recurrence of grade 4 toxicity after 7 days of nazartinib monotherapy at ↓ 1 dose level, resume capmatinib at the same dose level
 

Febrile Neutropenia	
ANC < 1000/mm  and a single temperature of >38.3°C (101°F) or a sustained temperature of ≥38°C (100.4°F) for more than one hour	
Omit study treatment until resolved, then resume nazartinib at the same dose level:
 
 
• If resolved in ≤ 7 days, resume capmatinib treatment at ↓ 1 dose level
 
• If resolved in > 7 days, permanently discontinue capmatinib treatment
 
• If recurrence during nazartinib monotherapy, omit nazartinib until resolved, then resume nazartinib ↓ 1 dose level and capmatinib at ↓ 1 dose level
 

Platelet count decreased (Thrombocytopenia)	
Grade 1 (PLT < LLN - 75,000/mm  ; < LLN - 75 x 10  /L)	Maintain dose levels of nazartinib and capmatinib
Grade 2 (PLT < 75,000 - 50,000/mm  ; < 75 - 50 x 10  /L)	Maintain dose levels of nazartinib and capmatinib
Grade 3 (PLT < 50,000 - 25,000/mm  )	Omit study treatment until resolved to ≤ grade 2, then resume nazartinib at the same dose level:

Worst toxicity CTCAE a Grade (value)	Recommendation

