	
 
• If fully resolved in ≤ 7 days, then resume capmatinib at same dose level
 
• If fully resolved in > 7 days, then resume capmatinib ↓ 1 dose level
 
• If recurrence of grade 3 toxicity during nazartinib monotherapy, omit study treatment until resolved to ≤ grade 2, then resume nazartinib ↓ 1 dose level, resume capmatinib at same dose level
 

Grade 4 (PLT < 25,000/mm  )	
Omit study treatment until resolved to ≤ grade 2, then resume nazartinib at the same dose level:
 
 
• If no recurrence of grade 3 or higher toxicity after 7 days of nazartinib monotherapy, resume capmatinib at ↓ 1 dose level
 
• If recurrence of grade 3 or higher toxicity on maintained dose of nazartinib and ↓ 1 dose level of capmatinib, omit study treatment until resolved to ≤ grade 2, then ↓ 1 dose level of nazartinib and maintain dose level of capmatinib (i.e., both study drugs ↓ 1 dose level from dose levels at initial occurrence of grade 4 AE)
 
• If recurrence of grade 3 or higher toxicity during nazartinib monotherapy, omit study treatment until resolved to ≤ grade 2, then resume nazartinib ↓ 1 dose level
 
• If no recurrence of grade 3 or higher toxicity after 7 days of nazartinib monotherapy at ↓ 1 dose level, resume capmatinib at ↓ 1 dose level
 

Hemoglobin decreased (Anemia)	
Grade 1 (Hgb < LLN - 10.0 g/dL; < LLN - 6.2 mmol/L; < LLN - 100 g/L)	Maintain dose levels of nazartinib and capmatinib
Grade 2 (Hgb < 10.0 - 8.0 g/dL; < 6.2 - 4.9 mmol/L; < 100 - 80 g/L)	Maintain dose level of nazartinib and capmatinib
Grade 3 (Hgb < 8 g/dL)	
Omit study treatment until resolved to ≤ grade 2, then resume at same dose levels of nazartinib:
 
 
• If fully resolved in ≤ 7 days, then resume capmatinib at same dose level
 
• If fully resolved in > 7 days, then resume capmatinib at ↓ 1 dose level
 
• If recurrence of grade 3 toxicity during nazartinib monotherapy, omit study treatment until resolved to ≤ grade 2, then resume nazartinib ↓ 1 dose level and resume capmatinib at same dose level
 

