Grade 4 (life-threatening consequences; urgent intervention indicated)	
Omit study treatment until resolved to ≤ grade 2, then resume same dose level of nazartinib and re-evaluate in 7 days, or sooner if clinically indicated
 
 
• If no recurrence of grade 3 or higher toxicity after 7 days of nazartinib monotherapy, resume capmatinib at ↓ 1 dose level
 
• If recurrence of grade 3 or higher toxicity during nazartinib monotherapy, omit study treatment until resolved to ≤ grade 2, then resume at ↓ 1 dose level of nazartinib.
 
• If no recurrence of grade 3 or higher toxicity after 7 days of nazartinib monotherapy at ↓ 1 dose level, resume capmatinib at ↓ 1 dose level
 

RENAL	
Serum creatinine	
Grade 1 (> ULN - 1.5 x ULN)	Maintain dose levels of nazartinib and capmatinib
Grade 2 (> 1.5 and ≤ 3.0 x baseline; or > 1.5 and ≤ 3 x ULN)	Omit study treatment until resolved to ≤ grade 1 or baseline, then resume treatment at the same dose level of nazartinib and capmatinib
Grade 3 (> 3.0 x baseline; or > 3.0 and ≤ 6.0 x ULN)	Omit study treatment until resolved to ≤ grade 1, then resume nazartinib at the same dose level:

Worst toxicity CTCAE a Grade (value)	Recommendation
	
 
• If no recurrence of grade 3 toxicity after 7 days of nazartinib monotherapy, resume capmatinib at ↓ 1 dose level
 
• If recurrence of grade 3 toxicity on maintained dose of nazartinib and ↓ 1 dose level of capmatinib, omit study treatment until resolved to ≤ grade 1, then resume nazartinib at same dose level and Capmatinib ↓ 1 dose level
 
• If recurrence of grade 3 toxicity during nazartinib monotherapy, omit study treatment until resolved to ≤ grade 1 or baseline, then resume nazartinib ↓ 1 dose level
 
• If no recurrence of grade 3 toxicity after 7 days of nazartinib monotherapy at ↓ 1 dose level, resume capmatinib at ↓ 1 dose level
 

Grade 4 (> 6.0 × ULN)	Discontinue capmatinib permanently and omit nazartinib until resolved to ≤ grade 1 or baseline, then resume nazartinib at same dose level.
HEPATICb	
Isolated Total Bilirubin elevation (for participants with Gilbert Syndrome these dose modifications apply to changes in direct [conjugated] bilirubin only)	
Grade 1 (> ULN – 1.5 × ULN)	Maintain nazartinib and capmatinib dose level

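### The last Grade 4 neutropenia step in Table 6-7 lets capmatinib restart at a neutrophil count for which the same row orders treatment to be withheld

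*Protocol*

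**What the plan says.** All the text at issue is in Protocol section 6.3.1 and its Table 6-7, which governs dose changes for nazartinib plus capmatinib.

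- **Grade 4 neutropenia (ANC <500/mm³), last step:** "If no recurrence of grade 4 toxicity after 7 days of nazartinib monotherapy at ↓ 1 dose level, resume capmatinib".
- **Grade 4 neutropenia, the step before it:** "If recurrence of grade 3 or higher toxicity during nazartinib monotherapy, omit study treatment until resolved to ≤ grade 2", after which nazartinib resumes one level lower.
- **Grade 3 neutropenia (ANC 500 to <1000/mm³), opening instruction:** "Omit study treatment until resolved to ≤ grade 2, then resume nazartinib at the same dose level".
- **Grade 3 neutropenia, last step:** "If no recurrence of grade 3 toxicity after 7 days of nazartinib monotherapy at ↓ 1 dose level, resume capmatinib at same dose level".
- **Grade 4 thrombocytopenia and Grade 4 anemia, matching step:** "If no recurrence of grade 3 or higher toxicity after 7 days of nazartinib monotherapy at ↓ 1 dose level, resume capmatinib".
- **Section 6.3.1, general rule:** the instruction, which is mandatory, is to "discontinue treatment with nazartinib and capmatinib if, after treatment is resumed at a lower dose, the toxicity recurs with the same or worse severity".

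Section 6.3.1 describes the table as recommendations and allows case-by-case exceptions after discussion between the sponsor and the investigator.

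**The concern.** The first three steps of the Grade 4 neutropenia row use one threshold, grade 3 or higher. The fourth, which decides whether the second drug is added back on reduced nazartinib, uses a different one: grade 4 only. Grade 3 neutropenia falls between the two thresholds, so the row gives opposite directions for it.

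The participant in question has already had Grade 4 neutropenia on the combination and a further event of grade 3 or higher on nazartinib alone. If Grade 3 neutropenia then appears on reduced nazartinib, the site has to choose between withholding treatment and adding a second drug. Group 5 participants can reach this table, because they may receive the combination after progressing on capmatinib alone.

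**Working it through.** No calculation in the plan bears on this, so the check compares the instructions directly.

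**Step 1. Apply the row to a participant on nazartinib alone, one level lower, at the 7-day point.**

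| ANC (/mm³) | Grade | Third step (withhold at grade 3 or higher) | Fourth step (restart if no grade 4) | Result |
|---|---|---|---|---|
| ≥1000 | 2 or lower | not triggered | met: add capmatinib | consistent |
| 500 to <1000 | 3 | triggered: withhold | met: add capmatinib | **contradictory** |
| <500 | 4 | triggered: withhold | not met | consistent |

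**Step 2. Look for another rule that settles the middle band.**

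- The Grade 3 neutropenia row orders omission at that ANC. It agrees with the third step and contradicts the fourth.
- The general rule in section 6.3.1 depends on the event that led to the nazartinib reduction. If that event was Grade 3, a further Grade 3 at the lower dose is the same severity and both drugs must stop. If it was Grade 4, the further Grade 3 is milder and the rule does not apply. It therefore either contradicts the fourth step or says nothing.
- Two notes on which toxicity governs point different ways. The note under Table 6-6 looks to the worst toxicity at the last dose, which leads to the Grade 3 row. The closing note to Table 6-7 looks to the worst preceding toxicity, which keeps the participant in the Grade 4 row.

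**Step 3. Compare with the same step in other rows.**

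| Row | Restart on the reduced drug requires |
|---|---|
| Neutropenia Grade 3 | no grade 3 |
| Neutropenia Grade 4 | no grade 4 |
| Thrombocytopenia Grade 4 | no grade 3 or higher |
| Anemia Grade 4 | no grade 3 or higher |

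The test becomes looser as the index neutropenia becomes worse, and it differs from both other Grade 4 rows that contain this step.

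**Step 4. Count every such step in Table 6-7** (7 days of one drug alone at one level lower, then the other drug returns).

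- Grade 3 named: neutropenia G3, creatinine, bilirubin, amylase/lipase, hypertension, diarrhea, nausea, vomiting, rash, fatigue, edema, other events = 12
- Grade 3 or higher named: thrombocytopenia G4, anemia G4 = 2
- No grade named: AST/ALT = 1
- Grade 4 named: neutropenia G4 = 1
- Total: 12 + 2 + 1 + 1 = 16

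**Step 5. Test the correction.** With grade 3 or higher as the trigger, the fourth step is not met at ANC 500 to <1000/mm³. The middle band in Step 1 then reads withhold and do not restart, and the contradiction is gone.

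**The case against.** The strongest reply is that the steps run in sequence: the third covers nazartinib at its unchanged dose and ends by reducing it, and the fourth governs the reduced-dose period, so they never overlap. The third step sets no such limit. Even on that reading the Grade 3 row still orders omission at the same count, and the Grade 4 row itself would contain nothing to stop capmatinib being added.

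A second reply is that the protocol already leads to the safe action, through the note on the last dose and the mandatory stopping rule in section 6.3.1. This holds in part. Where the stopping rule applies, it should override a recommendation. It does not apply when the event behind the nazartinib reduction was Grade 4, and the note on the last dose concerns dose reduction rather than restart.

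Third, one in 16 overstates how unusual the step is. This stands. Twelve of the other steps sit in rows indexed at Grade 3 or Grade ≥3, so they largely repeat their own index grade. The fair comparison is with the two other Grade 4 rows, which makes this step one of three.

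Fourth, reach is small. This also stands. As of the Amendment 07 rationale, nobody in Phase Ib or Groups 1 to 4 was still on treatment. Only Group 5 participants who progress, choose the combination and sign a separate consent are exposed, and each would need three successive neutropenia events. If Grade 3 is seen before day 7 and treatment is withheld then, the 7-day condition is not met, so the conflict arises mainly when Grade 3 is first found at the 7-day check.

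**Conclusion.** The concern holds. As written, the last Grade 4 neutropenia step permits adding capmatinib at an ANC of 500 to <1000/mm³, where the preceding step and the Grade 3 row both withhold treatment. The looser test after the worse event, and the stricter wording in both comparable Grade 4 rows, point to a drafting slip rather than a deliberate choice.

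The conclusion rests on reading the third step as written, without a dose limit. If it is confined to unchanged-dose nazartinib, the conflict with the Grade 3 row remains. The number of participants affected cannot be estimated, because the available text gives no neutropenia frequency for the combination; it is likely to be very small. The primary Group 5 endpoint, response on capmatinib monotherapy, is not affected. This should be corrected because it is a contradictory safety instruction, not because it threatens the trial's inference.

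**What to change.** In the last step of the Grade 4 neutropenia row of Table 6-7, change the restart condition from no recurrence of grade 4 to no recurrence of grade 3 or higher. This aligns the threshold with the rest of the row and with the Grade 4 thrombocytopenia and anemia rows. The cost is one phrase in the protocol table, with no added visits or laboratory tests.

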**Table 6-4 Criteria for defining dose-limiting toxicities in the Phase Ib part**

Toxicity	Any of the following criteria:
Hematology	Any hematologic toxicity = grade 3, lasting for > 7 consecutive days
	Any hematologic toxicity $\geq$ grade 4 (of any duration)
	Febrile neutropenia (ANC < $1.0 \times 10^9/L$ or $1000/mm^3$ with a single temperature of $>38.3^\circ C$ ( $101^\circ F$ ) or a sustained temperature of $\geq 38^\circ C$ ( $100.4^\circ F$ ) for more than one hour.
Renal	Serum creatinine $\geq$ grade 3 ( $\geq 3.0 \times$ baseline or $> 3.0 - 6.0 \times$ ULN)
Hepatic	Total bilirubin $\geq$ grade 3 ( $> 3 \times$ ULN)
	AST or ALT = grade 3 ( $>5.0-20.0 \times$ ULN) for $>7$ consecutive days AST or ALT = grade 4 ( $>20.0 \times$ ULN)
	For participants with normal baseline AST and ALT and total bilirubin value: AST or ALT $>3.0 \times$ ULN combined* with total bilirubin $>2.0 \times$ ULN without evidence of cholestasis** OR For participants with abnormal baseline AST or ALT or total bilirubin value: [AST or ALT $>2 \times$ baseline AND $> 3.0 \times$ ULN] OR [AST or ALT $> 8.0 \times$ ULN], whichever is lower, combined with [total bilirubin $> 2 \times$ baseline AND $> 2.0 \times$ ULN]
Pancreas	Asymptomatic serum amylase or lipase grade 3 ( $>2.0 - 5.0 \times$ ULN) occurring for $> 14$ consecutive days
	Asymptomatic serum amylase or lipase grade 4 ( $>5.0 \times$ ULN) of any duration
	Symptomatic serum amylase or lipase elevation, medical intervention required
Neurologic	Any neurological abnormality or toxicity $\geq$ grade 2
Diarrhea	$\geq$ grade 3 despite optimal treatment
Skin and subcutaneous tissue disorders	$\geq$ grade 3 despite 7 consecutive days of optimal treatment
Respiratory	$\geq$ grade 2 pneumonitis or interstitial lung disease (ILD) without infection etiology
Other adverse events	Any adverse event $\geq$ grade 3 Single event or multiple occurrences of the same event that lead to a dosing interruption of $> 7$ days in Cycle 1, may be considered to be DLTs by the Investigators and Novartis, even if not CTCAE grade 3 or higher

Toxicity	Any of the following criteria:
* "Combined" defined as: total bilirubin increase to the defined threshold concurrently with ALT/AST increase to the defined threshold	
** "Cholestasis" defined as: ALP elevation >2xULN and R value (ALT/ALP in x ULN) < 2] in participants without bone metastasis, or elevation of ALP liver fraction in participants with bone metastasis)	

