Grade 3 (PLT < 50,000 - 25,000/mm  ; < 50 - 25 x 10  /L)	Omit dose until resolved to ≤ grade 2, then: 
 
• If fully resolved in ≤ 7 days, then resume at same dose level
 
• If resolved in > 7 days, then resume at ↓ 1 dose level
 

Grade 4 (PLT < 25,000/mm  ; < 25 x 10  /L)	Omit dose until resolved to ≤ grade 2, then resume at ↓ 1 dose level
Febrile Neutropenia	
ANC < 1000/mm  and a single temperature of >38.3°C (101°F) or a sustained temperature of ≥38°C (100.4°F) for more than one hour	Omit dose, then: 
 
• If resolved in ≤ 7 days, resume treatment at resume at ↓ 1 dose level
 
• If resolved in > 7 days, permanently discontinue capmatinib treatment
 

Hemoglobin decreased (Anemia)	
Grade 1 (Hemoglobin [Hgb] < LLN - 10.0 g/dL; < LLN - 6.2 mmol/L; < LLN - 100 g/L)	Maintain dose level

Worst toxicity CTCAE Gradea during a cycle of therapy	Recommendation
Grade 2 (Hgb < 10.0 - 8.0 g/dL; < 6.2 – 4.9 mmol/L; < 100 - 80 g/L)	Maintain dose level
Grade 3 (Hgb < 8.0 g/dL; < 4.9 mmol/L; < 80 g/L; transfusion indicated)	Omit dose until resolved to ≤ grade 2, then: 
 
• If fully resolved in ≤ 7 days, resume at the same dose level
 
• If fully resolved in > 7 days, then resume at ↓ 1 dose level
 

Grade 4 (Life-threatening consequences; urgent intervention indicated)	Omit dose until resolved to ≤ grade 2 and then resume at ↓ 1 dose level If grade 4 toxicity recurs, permanently discontinue capmatinib treatment.
RENAL	
Serum creatinine	
Grade 1 (> ULN - 1.5 x ULN)	Maintain dose level
Grade 2 (> 1.5 - 3.0 x ULN)	Omit dose until resolved to ≤ grade 1 or baseline, then resume at the same dose level.
Grade 3 (> 3.0 - 6.0 x ULN)	Omit dose until resolved to ≤ grade 1 or baseline, then resume at ↓ 1 dose level.
Grade 4 (> 6.0 x ULN)	Permanently discontinue capmatinib treatment
HEPATIC	
Isolated Total Bilirubin elevation*	
Grade 1 (> ULN - 1.5 x ULN)	Maintain dose level
Grade 2 (> 1.5 - 3.0 x ULN)	Omit dose until resolved to ≤ grade 1, then 
 
• If fully resolved in ≤ 7 days, resume at same dose level.
 
• If resolved in > 7 days, resume at ↓ 1 dose level
 

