Grade 1 or 2	Maintain dose level, consider to initiate appropriate support medication. For any intolerable grade 2 (e.g. limiting instrumental activities of daily living), consider omitting the dose until resolved to ≤ grade 1, then resume either at same dose or ↓ 1 dose level.
Grade 3	Omit dose until resolved to ≤ grade 1, then resume at ↓ 1 dose level
Grade 4	Permanently discontinue capmatinib

All dose modifications should be based on the worst preceding toxicity.
 
a Common Toxicity Criteria for Adverse Events (CTCAE version 5.0).
 
b “Combined” defined as: total bilirubin increase to the defined threshold concurrently with ALT/AST increase to the defined threshold
 
c “Cholestasis” defined as: ALP elevation (> 2.0 x ULN and R value (ALT/ALP in x ULN) < 2.0) in participants without bone metastasis, or elevation of ALP liver fraction in participants with bone metastasis
 
d If combined elevations of AST or ALT and total bilirubin do not meet the defined thresholds, please follow the instructions for isolated elevation of total bilirubin and isolated elevation of AST/ALT, and take a conservative action based on the degree of the elevations (e.g. discontinue treatment at the situation when omit dose is needed for one parameter and discontinue treatment is required for another parameter). After all elevations resolve to the defined thresholds that allow treatment re-initiation, re-start the treatment either at the same dose or at one dose lower if meeting a criterion for dose reduction
 
* Note: If total bilirubin > 3.0 x ULN is due to the indirect (non-conjugated) component only, and hemolysis as the etiology has been ruled out as per institutional guidelines (e.g., review of peripheral blood smear and haptoglobin determination), then ↓ 1 dose level and continue treatment at the discretion of the investigator
 
** Note: antidiarrheal medication is recommended at the first sign of abdominal cramping, loose stools or overt diarrhea
 
*** During the whole duration of treatment with capmatinib, the participant is recommended to use precautionary measures against ultraviolet exposure (e.g., use of sunscreen, protective clothing and avoid sunbathing or using a solarium intensively)
	

**Table 6-9 Dose modifications for nazartinib (if capmatinib permanently discontinued and nazartinib continued as monotherapy)**

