Worst toxicity CTCAE a Grade (value) during a cycle of therapy	Recommendations
HEMATOLOGICAL	
Neutrophil count decreased (ANC) Neutropenia	
Grade 1 (ANC <LLN - 1500/mm  )	Maintain dose level
Grade 2 (ANC <1500 - 1000/mm  )	Maintain dose level
Grade 3 (ANC <1000 - 500/mm  )	Omit dose until resolved ≤ Grade 2, then maintain dose level
Grade 4 (ANC <500/mm  )	Recommendation: omit dose until resolved to ≤ Grade 2, then resume at ↓ 1 dose level
Febrile Neutropenia	
(ANC <1.0 x 10  /L, fever ≥ 38.5°C)	Recommendation: omit dose until resolved, then resume at ↓ 1 dose level
Thrombocytopenia	
Grade 1 (PLT <LLN - 75,000/mm  )	May maintain dose level
Grade 2 (PLT <75,000 - 50,000/mm  )	May maintain dose level
Grade 3 (PLT <50,000 - 25,000/mm  )	
 
Recommendation: omit dose until resolved to ≤ Grade 1, then:
 
If fully resolved in ≤ 7 days, then resume at same dose level
 
If fully resolved in >7 days, then resume at ↓ 1 dose level
 

Grade 4 (PLT <25,000/mm  )	Recommendation: omit dose until resolved to ≤ Grade 1, then resume at ↓ 1 dose level
RENAL	
Serum creatinine	
Grade 1 (>ULN - 1.5 x ULN)-	May maintain dose level
Grade 2 (>1.5 – 3.0 x ULN)	Recommendation: omit dose until resolved to ≤ Grade 1 or baseline, then resume at same dose level
Grade 3 (>3.0 – 6.0 x ULN)	Recommendation: omit dose and discontinue nazartinib
Grade 4 (>6.0 x ULN)	Recommendation: omit dose and discontinue nazartinib
HEPATICb	
Isolated Total Bilirubin (for participant s with Gilbert Syndrome these dose modifications apply to changes in direct [conjugated] bilirubin only)	
Grade 1 (>ULN - 1.5 x ULN)	Recommendation: maintain dose level
Grade 2 (>1.5 - 3.0 x ULN)	Recommendation: omit dose. Monitor LFTs c weekly, or more frequently if clinically indicated until resolved to ≤ 1.5 x ULN, then: 
 
If fully resolved in ≤14 days, then resume at same dose level
 
If fully resolved in >14 days, then resume at ↓ 1 dose level
 

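### Minor: the febrile neutropenia row of Table 6-7 stops capmatinib permanently in one bullet and restarts it in the next

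*Protocol*

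**What the plan says.** Table 6-7 (dose changes on the combination) handles febrile neutropenia by holding both drugs until resolution and then resuming nazartinib at the same level. Three bullets follow.

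- Bullet 1, resolution within 7 days: capmatinib resumes one level lower.
- Bullet 2, resolution in more than "7 days, permanently discontinue capmatinib treatment".
- Bullet 3: "If recurrence during nazartinib monotherapy, omit nazartinib until resolved, then resume nazartinib ↓ 1 dose level and capmatinib at ↓ 1 dose level".

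Table 6-9 carries the title "Dose modifications for nazartinib (if capmatinib permanently discontinued and nazartinib continued as monotherapy". Its febrile neutropenia row says only "Recommendation: omit dose until resolved, then resume at ↓ 1 dose level", with nothing about capmatinib. Table 6-8 (capmatinib alone) repeats the permanent stop after more than 7 days and has no restart bullet.

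The fever criterion also differs. Tables 6-7 and 6-8 use "a single temperature of >38.3°C (101°F) or a sustained temperature of ≥38°C (100.4°F) for more than one hour", and Table 6-4 uses the same thresholds for dose-limiting toxicity. Table 6-9 requires a fever of at least 38.5°C.

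**The concern.** Bullet 2 creates a participant on nazartinib monotherapy whose capmatinib has been stopped permanently. Bullet 3 is triggered by recurrence during nazartinib monotherapy and is not restricted to the branch in bullet 1. As written it covers the bullet 2 participant and tells the site to resume the drug that the preceding bullet ended.

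This is an inconsistency of wording in a safety table; no design decision is in question. It matters because the conflict arises after a second febrile neutropenia episode, when a site needs a single answer.

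**Working it through.** There is no planned figure to reproduce; the check sets the instructions side by side.

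**1. Which participants bullet 3 reaches.** Bullet 1 restarts capmatinib without stating any nazartinib-only interval. Bullet 2 is the only branch of this row that explicitly leaves nazartinib alone. Where Table 6-7 wants a trial period on nazartinib before capmatinib returns, several rows say so, for example Grade 4 neutropenia, Grade 4 platelets, Grade 4 anemia and Grade 3 creatinine, each with a 7-day period.

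**2. Whether this is a convention of the table.** Four graded rows or branches of Table 6-7 stop capmatinib permanently and keep nazartinib: febrile neutropenia beyond 7 days, creatinine Grade 4, amylase/lipase Grade 4 and peripheral edema Grade 4. (A note under amylase/lipase also stops capmatinib for pancreatitis of Grade 3 or higher.) A capmatinib restart is instructed in 1 of the 4, the febrile neutropenia row. The Grade 3 platelet and Grade 3 anemia rows have the same three-bullet shape but no permanent stop, so their third bullet contradicts nothing.

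**3. Capmatinib dose after the second episode, bullet 2 participant.** Levels are from Table 6-5. All three are possible at entry to the Group 5 combination stage, because section 6.1.1 carries over the capmatinib dose from the monotherapy period.

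| Capmatinib dose at first episode | Bullet 2 and Table 6-9 | Bullet 3 (one level lower) |
|---|---|---|
| 400 mg b.i.d. | 0 | 300 mg b.i.d. |
| 300 mg b.i.d. | 0 | 200 mg b.i.d. |
| 200 mg b.i.d. | 0 | no listed level; section 6.3.1 allows only two reductions |

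Nazartinib goes down one level under either table.

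**4. Fever definition.** The definitions disagree for a single reading above 38.3°C but below 38.5°C, and for 38.0°C to below 38.5°C sustained for more than one hour. In that band a participant governed by Table 6-9 falls to its plain neutropenia rows.

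- ANC 500 to below 1000/mm³ (Grade 3 row): "Omit dose until resolved ≤ Grade 2, then maintain dose level". The other tables' definition would make this febrile neutropenia, resumed one level lower. By Table 6-6 that is 100 against 75 mg q.d. if there was no earlier reduction.
- ANC below 500/mm³ (Grade 4 row): resumed one level lower under both, so nothing changes.

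Nazartinib is interrupted in every case; only the resumption level differs, and only in the first band.

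**The case against.** The strongest reply is that bullet 3 is loose template wording with a clear intent. In the Grade 3 platelet, anemia, AST/ALT and fatigue rows capmatinib resumes in both time branches, yet a later bullet still speaks of recurrence on nazartinib alone. There the phrase can only mean the interval before capmatinib is restarted, so bullet 3 probably continues bullet 1. Once capmatinib is permanently stopped, Table 6-9 applies by its title, and the more specific table should govern.

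Section 6.3.1 adds safeguards. In exceptional cases and after sponsor discussion, "participants may be allowed to continue treatment or resume treatment with only one of the investigational drugs", so the sponsor should already be involved. A drug-related interruption of more than 21 days requires discontinuation unless described otherwise. With capmatinib already off for more than 7 days, fewer than 21 − 7 = 14 days would remain for the nazartinib restart, the second episode and its resolution.

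The point about intent stands. None of it removes the restart instruction. The comparison rows contain no permanent stop to contradict. Sponsor discussion does not say which bullet is the rule, and the 21-day limit gives way wherever something else is described, which bullet 3 arguably does. The 6.3.1 rule that ends both drugs applies to recurrence after resumption at a lower dose, whereas here nazartinib was resumed at the same dose. It is also fair to say that the fever threshold is a separate discrepancy and lends no support to the capmatinib point.

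**Conclusion.** The row is wrong as written, at minor severity. For one sequence of events (a first episode on the combination that takes more than 7 days to resolve, then a recurrence on nazartinib alone) it gives two incompatible capmatinib instructions: none, or 300 or 200 mg b.i.d., or a level that does not exist. The fever discrepancy is real but narrower.

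Exposure is small. No Group 1 to 4 participant was on treatment as of 20-Oct-2021, so only Group 5 participants (about 30 planned) who go on to the optional combination are affected. The primary endpoint is ORR on capmatinib monotherapy and is unaffected. Table 6-7 gives recommendations, and the sponsor can be consulted. The documents give no rate for this sequence and none is assumed. The conclusion rests on the literal text; the likely intent is that Table 6-9 takes over after bullet 2.

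**What to change.** In Table 6-7, febrile neutropenia, limit the capmatinib restart in bullet 3 to participants whose capmatinib was not permanently discontinued, meaning that the first episode resolved within 7 days and capmatinib had not yet been restarted. Add that participants with permanently discontinued capmatinib follow Table 6-9. In the same edit, replace the 38.5°C criterion in Table 6-9 with the definition used in Tables 6-4, 6-7 and 6-8.

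The cost is wording only: one bullet and one table cell, through the next amendment or a clarification letter to sites, with no added visits or tests.
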